- C. SAFTEE: The SAFTEE is a technique for the systematic assessment of side effects in clinical trials. The SAFTEE will be reviewed by the study nurse and specific symptoms, as well as severity, will be recorded. The SAFTEE will be administered weekly.

Data Analysis Methods:

A. Sample Size and Power Analysis:

For this pilot study, we will recruit a total of 200 subjects, 100 subjects in each treatment arm. No previous studies have examined the influence of BUP/NLX dose on treatment outcomes in prescription-opioid dependent individuals. Our sample of 200 will require an effect size of .25 to detect differences between the two treatment groups for the number of opioid positive urines during the treatment period.

B. Statistical analysis:

The principal analyses will be done on the modified intention to treat sample, that is, subjects receiving at least one dose of BUP/NLX. First, we will determine the success of the randomization by comparing the two treatment groups on socio-demographic and baseline clinical characteristics using chi-square for categorical variables and ANOVA for continuous variables. Second, survival analysis will be used to determine differences between experimental groups in treatment retention. Third, random regression analyses (HLM), (Hedeker and Gibbons 1996) will be conducted to examine if the change in opioid use behavior over time varies as a function of the treatment factors.

Risks and Benefits:

Potential risks

1. Buprenorphine: Buprenorphine, formulated as a sublingual tablet, is available alone or in combination tablet containing buprenorphine and naloxone in a ratio of 4:1. The doses of buprenorphine/naloxone used here are within the recommended guidelines of the manufacturer (4-24 mg/day). In this study, combination tablet will be used, since it is less likely to be diverted than the buprenorphine alone formulation. Common side effects of buprenorphine/naloxone include abdominal pain, constipation, nausea, vomiting, headache sweating, sedation, and allergic reaction. Uncommon but more serious adverse effects of buprenorphine/naloxone include hepatic abnormalities, orthostatic hypotension and respiratory depression.
2. Buprenorphine/Naloxone detoxification: Detoxification from buprenorphine/naloxone can produce signs and symptoms of opiate withdrawal, including nasal congestion, abdominal symptoms, anxiety, myalgia, insomnia, sweating, and diarrhea.

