- c. Data and Safety Monitoring Plan: The study will be monitored by a Data and Safety Monitoring Board (DSMB). Risks associated with participating in this protocol are moderate. There is adequate surveillance and protection to discover adverse events promptly and keep their effects minimal. The Board will be composed of persons who are experienced in the conduct of clinical trials for the treatment of addictive disorders and who have appropriate expertise in substance abuse and psychopharmacology. There will be at least one physician on the board who is not directly involved in this trial, but who has the requisite expertise. In order for the DSMB to fulfill its mission of assuring the safety of human subjects and the scientific integrity of the study being conducted, the Board will review adverse event data no less than three times per year. During these meetings, the DSMB will review a table of adverse events at these four-month intervals. Following each DSMB meeting, written minutes will be prepared and distributed summarizing any recommendations, including any for interim analyses, as described above. These written reports will insure accurate preparation of any protocol amendments that might be necessary. After each DSMB meeting, this written report will describe all recommendations including additional safety steps. All serious adverse events such as deaths, hospitalizations, and unexpected toxicity will be reported to the IRB as well as our local hospital risk management committee under expedited reporting, i.e., immediately by telephone as the information is available to us, followed by written report within 48 hours. The procedures for written reporting include written documentation using the clinical notes related to the adverse event and specific forms detailing the event with a sign-off by all appropriate supervisory personnel. Communication of recommendations and decisions are made back to the investigator in a timely manner. These reports will also circulate to the DSMB.

Reporting of Adverse Events

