An adverse event is any physical or clinical change or disease experienced by the subject at any time during the course of the study, whether or not considered related to the use of the study drug. This includes the onset of new illness and the exacerbation of pre-existing conditions. Subjects will be questioned and / or examined by the investigator or his / her designee for evidence of adverse events. The questioning of subjects with regard to the possible occurrence of adverse events will be generalized such as, "How have you been feeling since your last visit?" The presence or absence of specific adverse events will not be solicited from subjects. All adverse events will be recorded in the subject's medical and / or research records. The onset and end dates, severity, and relationship to the study drug will be recorded for each adverse

event. Any action or outcome (e.g., hospitalization, discontinuation of therapy, etc.) will also be recorded for each adverse event.

All serious adverse events, whether or not deemed drug-related or expected, will be reported by the principal investigator or designee to the IRB within 24 hours (one working day) by telephone. A serious adverse event is any event that: is fatal, is life-threatening (life-threatening is defined as the patient was at immediate risk of death from the AE as it occurred), is significantly or permanently disabling, requires inpatient hospitalization or prolongs hospitalization, is a congenital anomaly or birth defect. Important medical events that may not result in death, be life-threatening, or require hospitalization may be considered a serious adverse drug experience when, based upon appropriate medical judgment, they may jeopardize the patient or subject, and may require medical or surgical intervention to prevent one of the outcomes listed in this definition. Serious adverse events will get reviewed immediately by the PI. Otherwise, this moderate risk study will be monitored quarterly by the PI and the members of the DSMB, and reported to the IRB if trends in AEs emerge.

Informed Consent:

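### The protocol bars soliciting specific adverse events yet schedules the SAFTEE at baseline and weekly, and no rule says whether SAFTEE symptoms reach the adverse event record or the DSMB table

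*Combined protocol and SAP*

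**What the plan says.** Three parts of the combined protocol and SAP bear on this.

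- **Reporting of Adverse Events.** The definition is broad: "An adverse event is any physical or clinical change or disease experienced by the subject", at any time in the study and whether or not attributed to study drug. On elicitation, "The questioning of subjects with regard to the possible occurrence of adverse events will be generalized such as" an open enquiry about how the participant has been since the last visit. Then: "The presence or absence of specific adverse events will not be solicited from subjects". Each event is to be recorded with its dates, severity and attribution. Apart from serious events, the IRB is told if a trend in adverse events appears.
- **Assessments.** The SAFTEE is in the baseline list and the weekly list, but not in the list for the 1, 3 and 6 month visits. Its description reads: "The SAFTEE is a technique for the systematic assessment of side effects in clinical trials". Further, "The SAFTEE will be reviewed by the study nurse and specific symptoms, as well as severity, will be recorded", and "The SAFTEE will be administered weekly".
- **Data and Safety Monitoring Plan.** The board meets at least three times a year, and "the DSMB will review a table of adverse events at these four-month intervals". The source of the table is not given.

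The statistical analysis section covers baseline comparability, retention and opioid use over time. It contains no safety analysis.

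**The concern.** A participant cannot go through a systematic weekly side-effect assessment while no specific event is solicited. One section describes a practice that the other rules out, and staff have no text telling them which governs the adverse event record.

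What is at stake is the content of the safety tables. Open-ended and structured questioning measure different things. Answers to an open question depend on what the participant thinks worth mentioning, and in an open-label comparison of a low and a high dose range that may be influenced by knowing the assignment. A structured instrument puts the same enquiry to both arms on the same schedule. If the DSMB sees only the first kind of data, the more uniform source is collected but not used for monitoring. If the two kinds are mixed without a rule, a count cannot be interpreted, because it depends on how each event came to light.

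**Working it through.** The documents give no adverse event rate and no safety sample size, so there is no plan figure to reproduce and no effect to calculate. The check is a comparison of the texts, plus a count of assessments.

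**1. Do the sections conflict?** The adverse event section requires general questioning and excludes solicitation of specific events. The SAFTEE section describes a systematic technique, administered weekly, that yields specific symptoms with severity. The weekly withdrawal scale also rates nausea/vomiting and sweating, both of which the protocol lists as side effects of the study drug. The non-solicitation sentence therefore does not describe the planned visits.

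**2. Is there a link between the SAFTEE and the adverse event record?** None is stated, and the text points two ways:

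- By the definition, a SAFTEE symptom that is new or worse than at baseline is a change and so an adverse event. The baseline SAFTEE would allow that judgement.
- By the elicitation rule, events come from general questioning, and a symptom found by structured enquiry falls outside it.

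The data items differ too. The adverse event record needs dates and attribution as well as severity. The SAFTEE section provides for symptom and severity only, and nobody is assigned to complete the rest.

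**3. What reaches the DSMB?** The table is described only as one of adverse events. If the elicitation rule governs, the table and the trend-based report to the IRB rest on open-question reports alone, and the SAFTEE appears in no stated table or analysis. If the definition governs, both kinds of event are in the table with nothing to tell them apart.

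**4. What happens after week 12?** The SAFTEE is not scheduled at the three follow-up visits. If adverse events are still collected there, as the whole-study definition implies, the open question is the only stated method of eliciting them. A table pooling both sources over time would change its method at the end of treatment. A fall in events at that point could reflect the method, or the end of study treatment, and the table could not separate the two.

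**5. How much data is concerned?** A participant who completes treatment has 1 baseline + 12 weekly = 13 SAFTEE assessments. With 200 participants the weekly ones number at most 12 × 200 = 2,400, and baseline adds up to 200, giving 2,600. These are ceilings that assume nobody leaves early, although the protocol provides for discharge and withdrawal. They count forms, not missed events or bias.

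**The case against.** The best defence is that the two sections govern different activities. The non-solicitation sentence concerns adverse event questioning, while the SAFTEE is a separate scheduled assessment, and both can be done at one visit. The SAFTEE section says symptoms are recorded, not that each is asked about. New or worsened symptoms already meet the adverse event definition, and all adverse events must be recorded. Both arms share one schedule, and serious events have their own expedited route.

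Much of this stands. The two methods can coexist, so they are unreconciled rather than incompatible. But the protocol does not offer that reconciliation, and reading a systematic, weekly-administered instrument as involving no specific enquiry is strained. Relying on the definition to bring SAFTEE symptoms in means setting aside the elicitation sentence, which is the contradiction itself.

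A reader might infer four stronger things that the documents do not support:

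- That a planned safety comparison between arms is damaged. None is specified.
- That the DSMB table draws on two sources. Its source is undefined, which is a different fault.
- That every SAFTEE symptom is an adverse event. A symptom present at baseline and unchanged is not a change.
- That the arms will be compared with bias. Open-label knowledge of dose could affect answers to a structured instrument as well as to an open question, and no differential effect is shown.

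**Conclusion.** The point holds as an unreconciled contradiction on elicitation, with no rule carrying SAFTEE symptoms into the adverse event record and no named source for the DSMB table. On the literal reading, safety monitoring in an open-label dose comparison would rest on open-question reports, and the systematically collected data would go unused.

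The size of any under-count or imbalance cannot be derived from the documents. The conclusion assumes that the SAFTEE involves asking about specific symptoms, which is the natural reading of its description, although its items are not reproduced. The follow-up concern further assumes that adverse events are recorded at those visits and pooled with those from treatment. The matter is confined to safety data: the sample size and the retention and opioid-use analyses do not depend on it. It should be corrected before data accumulate, because a rule chosen later in an unblinded trial would be chosen with the arms known.

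**What to change.** 1. Limit the non-solicitation sentence to the general adverse event question, and refer there to the SAFTEE as a separate, structured source.
2. State that SAFTEE symptoms new or worsened from baseline are solicited adverse events, collected on the same schedule in both arms, and say who completes their dates and attribution.
3. Name the source or sources of the DSMB table.
4. Show solicited and unsolicited events separately by arm in the DSMB and final tables. Show the treatment period apart from follow-up, where no SAFTEE is scheduled.

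The cost is protocol wording and one extra table from data already being collected. No visit or instrument is added.
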